### Secondary Endpoints

- Change in Resting Metabolic Rate/Resting Energy Expenditure
- Change in Hormone and Metabolic Markers in Blood including testosterone (free & total), growth hormone, insulin-like growth factor, leptin, insulin, thyroid hormones, cortisol and ghrelin and urinary creatinine and urinary iodine
- Change in Strength (all muscle groups)
- Change in Aerobic Fitness
- Change in Walking Economy

Change in and absolute values of Health Outcomes (blood pressure, serum cholesterol, fasting and 24-hour glucose concentration, and hydration status)

Change in Dietary Patterns

Change in Physical Activity and Structured Exercise

Change in Appetite

Baseline vitamin D intake and status and change in serum vitamin D

**4.2** *Describe any primary or secondary safety endpoints. These should be included for all studies that are greater than minimal risk. (Minimal risk: The probability and magnitude of harm or discomfort anticipated in the research that are not greater in and of themselves than those ordinarily encountered in daily life or during the performance of routine physical or psychological examinations or tests.):*

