## 8.0 Procedures Involved

### 8.1 Describe and explain the study design:

Sixteen men and sixteen women between the ages of 18 and 40 will be randomly assigned to the peanut intervention or control group (8 men/8 women/group). A computer program with a random number generator will be used by the study coordinator to assign male participants and female participants to the peanut or control group (i.e., each sex will be separately randomized).

As outlined in the table, eligible participants will undergo a 10-wk diet and training regimen designed to promote healthy weight gain. This will include increasing energy intake by 500 additional kcal/day (above their typical weight maintenance diet and accounting for energy requirements of resistance training) through provision of peanut-based whole foods/snacks or high-carbohydrate containing control snacks along

with a supervised rigorous resistance training regimen designed to promote muscle hypertrophy. After providing informed consent, participants will be randomly assigned to the peanut or control group based on sex. Outcome data will include assessment of body mass, total and regional body composition via DXA and body anthropometrics, skinfolds and somatotyping using the International Standards for Anthropometric Assessment (ISAK) (Stewart, Marfell-Jones et al. 2011) along with measures of resting metabolic rate (RMR), circulating hormones and serum/plasma biomarkers. The latter includes measurement of potentially important hormones/ biomarkers of anabolism, stress, overfeeding, and cardiometabolic health. Compliance to the nutrition and exercise regimen will be evaluated at regular intervals and include collection of 3-day food records (performed at baseline and 3-days prior to each assessment point) and physical activity data collected by digital technology (Garmin Vena SQ smart watch and My PT Hub app).

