**Resistance Training.** Participants will undergo rigorous resistance training three days/week in the NEM laboratory under close supervision. The following will be performed with weight machines (Nautilus) and free weights: leg press, squat, leg extension, leg flexion, toe raise, lat-pull down, dead lift, shoulder press, bench press, bicep curl, triceps extension and abdominal twist/crunch. The overall goal will be to have participants perform 10 sets of exercises that work the major muscle groups each week in accordance with a recently published position stand of the International Universities Strength and Conditioning Association (IUSCA) (Schoenfeld et al 2021) with slightly different set of exercises performed on each of the three days. Participants will begin with light to moderate resistance for 8-15 repetitions, after which resistance will be gradually increased in the next 5 workouts. After that, three to five sets of each exercise will be completed using modified methodology of Bartels et al (Kreider, Klesges et al. 1996) (previously shown to effectively promote weight gain) in accordance with the latest

guidelines for promoting muscle hypertrophy (Schoenfeld et al 2021). . Resistance will be adjusted upward after 8 repetitions are fully executed using proper technique. Participants engaged in a sport or military training activity will be instructed to maintain their normal training throughout the study.

Table 1. Overview of Data Collection

Overview of Data Collection	Baseline	3 wk	7 wk	11 wk
Body Mass (weight)	x	x	x	x
Body Composition by DXA and spot urine sample; Pregnancy test by urine in female participants	x	x	x	x
Skinfolds & circumferences	x			x
Resting metabolic rate-RMR	x	x		x
Blood via venipuncture and Urine vis 24-hr collection				
CBC and TSH	x			
Testosterone (free &total)	x	x	x	x
Growth Hormone	x	x	x	x
Insulin-like growth factor	x	x	x	x
Leptin	x	x	x	x
Insulin	x	x	x	x
Free T4	x	x	x	x
Cortisol	x			x
Ghrelin	x	x	x	x
Urinary creatinine and urinary iodine	x			x
Health outcomes				
Blood Pressure	x	x	x	x
Serum Lipids	x			x
Serum Vitamin D	x			x
Fasting blood glucose	x			x
Continuous glucose monitoring	x			x
Compliance and Fitness Testing				

Strength Testing	x			x
Aerobic Capacity (VO2max) and walking efficiency	x			x
Food Records and Appetite rating for 3-day	x	x	x	x
Vitamin D Food Frequency and Lifestyle Questionnaire	x			
Exercise tracking for 3-days (smart watch)	x	x	x	x
Daily snack tracking logs and exercise logs	↔	↔	↔	→

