**Baseline Laboratory Testing Session (approximately 2 hours and 30 minutes).**

All measurements will be performed in the morning after a 12-hour fast (no caffeine) with the participants instructed not to engage in heavy exercise for 36 hours prior to testing and to adequately hydrate the evening prior. This visit may be split into two shorter visits.

**Resting Metabolic Rate (RMR; also called Resting Energy Expenditure):** Participants will lay supine on a bed. A clear ventilated hood will be placed over their head, neck and shoulders and plastic drapes will be tucked under them to avoid leakage of air. Air will be pulled thru the hood with a pump and their expired air will be measured for oxygen and carbon dioxide content. The number of calories expended will be calculated using the total volume of air expired and the oxygen and carbon dioxide content. The ratio of carbon dioxide produced to oxygen consumed will be used to estimate carbohydrate and fat utilization.

**Blood Pressure:** Blood Pressure will be measured in the right arm using an automatic blood pressure monitor.

**Blood draws and hormone and metabolite analyses:** If blood was not drawn at the screening visit, it will be drawn immediately after the RMR for a CBC and analysis of TSH, testosterone (free and total), growth hormone, insulin-like growth factor, leptin, insulin, thyroid hormone, cortisol, ghrelin, blood glucose and other factors. Blood will be drawn by venipuncture as explained above for screening. Approximately 20-25 ml will be obtained during the screening/baseline visit.

**Body Weight Height and Composition:** Body weight and height will be measured on a digital physician's scale. Percent body fat and fat-free mass will be measured in all subjects via DXA scan.

**Urine sample and pregnancy test:** All participants will be required to provide a small cup of urine immediately before the DXA. The urine will be evaluated for hydration status

via specific density using a refractometer. A pregnancy test will be performed on the urine sample for female participants.

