**Dietary food records, exercise tracking, continuous glucose monitoring (CGM), and 24-hour urine collection:** Following laboratory testing, participants will be instructed on completing 3-day food records and exercise tracking, performing the CGM and completing the 24-hour urine collection. Participants will be asked to record all of the food they eat for 3 days, rate feelings of hunger and appetite using standardized appetite rating sheets, and wear a smart watch over this same time period. At baseline only, they will be asked to complete a food-frequency and lifestyle questionnaire specific to vitamin D intake/status simultaneously with the 3-day food records. The smart watch will use an app to measure heart rate and estimate energy expended during structured exercise or physical activity; this will be used to help estimate the participants total energy expenditure. It will be necessary to have the GPS function turned on during the collection of physical activity data but only data related to time, distance or intensity and not GPS coordinates will be downloaded or recorded. CGM will also coincide with the three-day food records using a device called a “Continuous Glucose Monitor” that is typically worn on the back of the upper arm. This requires that a small amount of interstitial fluid (0.5 microliters) be sampled every 15 minutes (96 times per day) throughout the course of the 3-day measurement. In addition, participants will be asked to collect urine for 24 hours during one day of this recall or within the first week of the study. Participants will void and discard the first morning urine sample and then collect all subsequent samples in provided clinical urine jugs for 24 hours, ending with the first sample upon waking the next day. Participants will schedule a time to drop off their urine during one of their resistant training sessions the first week or at a separate time, if it is more convenient. The instructions the participants will receive on using the Smart Watch, using CGM, and collecting the 24-hour urine are uploaded as an Addendum.

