#### Week 3 Laboratory Testing Session (approximately 75 minutes)

This session will be scheduled at the end of week 3/beginning of week 4 and will be performed in the morning after a 12-hour fast (no caffeine) with the participants instructed not to engage in heavy exercise for 36 hours prior to testing and to adequately

hydrate the evening prior. As outlined in the Table, all tests conducted as part of baseline testing will be performed except for CGM, 24-hour urine collection, walking economy and aerobic capacity. Blood will be drawn by venipuncture from a vein in the arm with the participant seated quietly in a phlebotomy chair. Blood and urine will be analyzed for selected hormones and metabolites (as outlined in the Table). Approximately 15 ml will be obtained for the Week 3 visit.

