#### Week 7 Laboratory Testing Session (approximately 60 minutes)

This session will be scheduled during week 7 and will be performed in the morning after a 12-hour fast (no caffeine) with the participants instructed not to engage in heavy exercise for 36 hours prior to testing and to adequately hydrate the evening prior. As outlined in the Table, all tests conducted as part of baseline testing will be performed except for the RMR, CGM, 24-hour urine collection, walking economy and aerobic capacity. Blood will be collected but analyzed only for selected hormones and metabolites. Blood will be drawn by venipuncture from a vein in the arm with the participant seated quietly in a phlebotomy chair. Blood will be analyzed for selected hormones and metabolites (as outlined in the Table). Approximately 15 ml will be obtained for The Week 7 visit.

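### On the plain reading, the 3-day smart-watch record follows the baseline visit but precedes the week 3 and 7 visits, where roughly 36% to 50% of its hours fall under a 36-hour ban on heavy exercise, so the records are not like for like

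*Combined protocol and SAP*

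**What the plan says.** Section 8.1 describes compliance monitoring as "collection of 3-day food records (performed at baseline and 3-days prior to each assessment point) and physical activity data collected by digital technology". The bracket that gives the dates belongs to the food records; the watch data come after it with no date of their own.

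For baseline, Section 8.2 gives the order: "Following laboratory testing, participants will be instructed on completing 3-day food records and exercise tracking, performing the CGM". The same paragraph asks participants to keep the food record, rate appetite and "wear a smart watch over this same time period". The baseline visit has its own 36-hour rule against heavy exercise, and "This visit may be split into two shorter visits".

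Table 1 has a row beginning "Exercise tracking for 3-days (smart watch", marked at baseline and weeks 3, 7 and 11. The row for the 3-day food record is marked at the same four points.

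The week 3 session has this condition: "performed in the morning after a 12-hour fast (no caffeine) with the participants instructed not to engage in heavy exercise for 36 hours prior". At week 7, participants are likewise "instructed not to engage in heavy exercise for 36 hours prior to testing". The week 11 session refers back to the baseline procedure.

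Section 4.1 lists "Change in Physical Activity and Structured Exercise" as a secondary endpoint. Section 8.2 also makes the watch data an input to estimated total energy expenditure. Section 5.2 has no rule that aligns the recording windows or allows for the rest period.

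**The concern.** A change score needs the same kind of window before and during the intervention. Here the baseline record starts once the pre-visit ban has ended, while the week 3 and 7 records appear to run into one. Participants must already be in sport, military or strength training (Section 12.2) and are told to keep that training up (Section 8.1). Heavy exercise is therefore much of what the watch should capture, and it is exactly what the ban suppresses.

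At stake are one named secondary endpoint, the energy-expenditure estimate and the activity part of the compliance check. Other sources help only in part. Supervised sessions are observed directly, daily logs cover other training during the intervention, and a screening questionnaire covers habitual activity. None of these is the same instrument before and during the intervention, so none supplies a like-for-like change.

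**Working it through.** The plan states no overlap figure, so there is none to reproduce.

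**Inputs from the protocol**
- Ban: 36 h ending at the visit (Section 8.2, week 3 and week 7).
- Window: 3 days = 72 h (Table 1).
- Visit time: morning, no clock hour given (Section 8.2).
- Supervised training: three days a week (Section 8.1), 60 to 75 minutes per session (Section 8.2).

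**Assumptions**
- Visits start between 06:00 and 10:00.
- The three days are either whole calendar days (-3 to -1) or the 72 h ending at the visit.

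**Step 1: share of the follow-up window under the ban.** With calendar days and a visit at clock hour v, v of the 36 banned hours fall on the visit day itself, outside the window. The share is (36 - v)/72.

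| Visit | Banned hours in window | Share |
|---|---|---|
| 06:00 | 30 | 30/72 = 41.7% |
| 08:00 | 28 | 28/72 = 38.9% |
| 10:00 | 26 | 26/72 = 36.1% |

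With a 72-hour window ending at the visit, the share is 36/72 = 50.0%.

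These are clock hours. Counting only assumed waking hours of 06:00 to 22:00 (48 h over three calendar days), the shares are 20/48 = 41.7%, 18/48 = 37.5% and 16/48 = 33.3% for visits at 06:00, 08:00 and 10:00. The night hours do not drive the result.

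**Step 2: share of the baseline window.** After an unsplit visit, the window opens when the ban has ended: 0/72 = 0%. If the visit is split, recording starts after the first part and the second part carries the same rule, a gap of g hours makes hours g - 36 to g restricted:
- g = 24: 24/72 = 33%
- g = 48 or 72: 36/72 = 50%
- g = 96: 12/72 = 17%

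The 0% therefore holds only for an unsplit visit, or for a record started after the second part.

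**Step 3: supervised exercise the ban alone could remove.** Only day -1 is wholly barred. If sessions on day -2 end before the ban starts that evening, at most one session per window is lost.
- None due on day -1, or the session is moved to a free day in the window: 0 min.
- Visit days unrelated to training days and nothing moved: 3/7 x 60 = 25.7 min to 3/7 x 75 = 32.1 min on average.
- Session due on day -1 and not made up in the window: 60 to 75 min.

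Habitual heavy training due that day would add an amount the documents do not give.

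**Step 4: check of the proposed window.** Days -5 to -3 end at midnight closing day -3. For an 08:00 visit the ban starts at 20:00 on day -2, which is 20 h later. The margin is 18 h for a 06:00 visit and 22 h for a 10:00 visit.

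**The case against.** **The watch timing is not stated.** The dating bracket in Section 8.1 covers food records only, and the phrase about the same period stands in the baseline text. Weeks 3 and 7 are described as repeating the baseline tests apart from listed exceptions, and neither the food record nor the tracking is among those exceptions. One could therefore place the follow-up records after those visits as well, which would remove the asymmetry. This stands as a caveat. It does not override the explicit placement in Section 8.1, and Table 1 pairs watch and food record at every time point. If the second reading is the intended one, the dates still need to be written down.

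**The direction is not shown.** This stands. The baseline window follows a treadmill test to exhaustion, and Section 17.1 warns of tiredness and muscle soreness lasting some days. Weeks 3 and 7 omit that test. Baseline activity may be lowered too, against the effect of the ban. A reader might infer that the plan understates a rise in activity; the documents do not support a net direction.

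**The loss may be nil.** This also stands. The team schedules both visits and sessions, and four of the seven days in a week have no supervised session the day before. The rule bars heavy exercise only, so lighter activity is still recorded. A reader might take the 36% to 50% as the share of exercise lost; it is a share of hours.

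**The consequence is narrow.** A reader might infer harm to the randomised comparison or to the weight and lean-mass results. Both arms follow the same schedule and rule, so no between-arm bias is shown. Nor is any effect on weight, lean mass, energy intake or glucose.

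**Conclusion.** The point holds as a minor one. Taking the watch window to be the food-record window, the week 3 and 7 records each carry a study-imposed rest period over roughly 36% to 50% of their hours, and an unsplit baseline record carries none. The lower figure assumes calendar days and a 10:00 visit; the upper assumes a 72-hour window ending at the visit. No single figure in that range follows from the protocol alone.

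The pre- and on-intervention watch records are thus not like for like for the activity endpoint and the energy-expenditure estimate. The ban's own contribution lies between zero and one supervised session per window plus unknown habitual training, and the possible after-effect of the maximal test leaves the sign of the net error open. Week 11 is left out of the claim: Section 8.1 puts its record before the visit, whereas the week 11 text points back to the baseline order.

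**What to change.** State the recording dates in Section 8.1 and in the baseline, week 3, week 7 and week 11 parts of Section 8.2:

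- Keep the follow-up watch and food record on days -5 to -3 before the visit, clear of the 36-hour ban.
- Keep the week 11 record inside the 10-week regimen. If the regimen ends on day 70, this means a visit no later than day 73.
- Start the baseline record a few days after the maximal exercise test, after the second part if the visit is split, and before training begins.
- Use the same weekday/weekend mix at each time point.

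Nothing here requires the glucose monitoring to move. Because Section 8.2 ties it to the food record, the sponsor should say whether it moves too. Where possible, place visits after a non-training day, since a session displaced by the ban could otherwise be brought forward into days -5 to -3 and inflate that record.

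The cost is small: no added visits or tests. The records would no longer run right up to the fasting measures, the watch and forms must be handed out earlier, and baseline may lengthen by a few days.

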### 8.2 Provide a description of:

- *All research procedures being performed*
- *If the study has more than one procedure, session, and/or subject population, describe each procedure, session, and/or study population separately. For complex studies, you are encouraged to include a figure or chart.*

#### Phone Screen

Those who respond to the investigation's advertisements will be scheduled to complete a brief telephone (or HIPAA-compliant Zoom) screening to confirm basic eligibility criteria. Participants will be made fully aware of the eligibility criteria, time commitment, possible risks and their right to withdraw from the study at any time. A phone screening script and phone screening data collection form (uploaded) will be used for phone screening and will conclude with a brief oral diet history performed by a research team member who is also a registered dietitian nutritionist.

#### Baseline Screening (approximately 45 minutes)

Informed Consent: Participants will be provided an informed consent form following the phone screening and in advance of coming to the laboratory.

Health History: Subjects will be asked to complete a standard health/medical history questionnaire, which will be used to screen for health issues (e.g., coronary or congenital heart disease) or other reasons (medications which influence study results) that would preclude participation (see uploaded Health History Screening Questionnaire). This questionnaire has been used by [name] for clinical studies for the past 17 years.

Physical Activity: Subjects will be asked to complete a questionnaire regarding habitual physical activity and exercise.

Skinfolds: Skinfolds will be measured at specific anatomical sites that include the triceps, subscapular, biceps, iliac crest, supraspinale, abdominale, front thigh, and medial calf using Harpenden skinfold calipers according to ISAK procedures with the sum of skinfolds used as the outcome variable. Anthropometric breadths and girths will be

obtained using a small sliding caliper and a flexible steel tape measure at the epicondylar humerus, epicondylar femur, midarm (relaxed and flexed), waist, hip, and calf. These will be used both as outcome variables and for initial somatotyping at baseline. This will be done by a trained investigator.

**Blood Draw:** If the participant is able to come into the laboratory after a 12-hour overnight fast, blood will be drawn by venipuncture for the following: a CBC, TSH, testosterone (free and total), growth hormone, insulin-like growth factor, leptin, insulin, thyroid hormone, cortisol, ghrelin, blood glucose, and serum cholesterol. Blood will be collected during the baseline session if the participant is not fasted as outlined below. In total, blood will be drawn four times during the study by venipuncture from a vein in the arm. These include baseline, and at 3, 7 and 11 weeks as explained below. Blood will be drawn with the participant seated quietly in a phlebotomy chair. Approximately 20-25 ml will be obtained for screening/baseline.

**Baseline Laboratory Testing Session (approximately 2 hours and 30 minutes).**

All measurements will be performed in the morning after a 12-hour fast (no caffeine) with the participants instructed not to engage in heavy exercise for 36 hours prior to testing and to adequately hydrate the evening prior. This visit may be split into two shorter visits.

**Resting Metabolic Rate (RMR; also called Resting Energy Expenditure):** Participants will lay supine on a bed. A clear ventilated hood will be placed over their head, neck and shoulders and plastic drapes will be tucked under them to avoid leakage of air. Air will be pulled thru the hood with a pump and their expired air will be measured for oxygen and carbon dioxide content. The number of calories expended will be calculated using the total volume of air expired and the oxygen and carbon dioxide content. The ratio of carbon dioxide produced to oxygen consumed will be used to estimate carbohydrate and fat utilization.

**Blood Pressure:** Blood Pressure will be measured in the right arm using an automatic blood pressure monitor.

**Blood draws and hormone and metabolite analyses:** If blood was not drawn at the screening visit, it will be drawn immediately after the RMR for a CBC and analysis of TSH, testosterone (free and total), growth hormone, insulin-like growth factor, leptin, insulin, thyroid hormone, cortisol, ghrelin, blood glucose and other factors. Blood will be drawn by venipuncture as explained above for screening. Approximately 20-25 ml will be obtained during the screening/baseline visit.

**Body Weight Height and Composition:** Body weight and height will be measured on a digital physician's scale. Percent body fat and fat-free mass will be measured in all subjects via DXA scan.

**Urine sample and pregnancy test:** All participants will be required to provide a small cup of urine immediately before the DXA. The urine will be evaluated for hydration status

via specific density using a refractometer. A pregnancy test will be performed on the urine sample for female participants.

**Walking Economy and Aerobic capacity (VO2max):** A graded exercise test will be performed on a treadmill to assess aerobic fitness via indirect calorimetry (Parvo Medics TrueOne 2400). Heart rate will be measured during the test by a heart rate strap and sensor. The exercise test will consist of walking or running on the treadmill starting at a self-selected pace with the grade or speed increasing every min until the participant reaches volitional exhaustion and can no longer continue. The test will begin with a walking economy test in which the participant walks for 4-minutes at 2.5, 3 and 3.5 mph. The last two minutes of oxygen consumption and carbon dioxide production data will be used to determine metabolic economy (ml oxygen consumed per kg body weight per minute relative to the set work performed). Following cumulation of the standard economy test, the workload will be increased each minute by increasing treadmill speed or grade by 0.5 mph or 2.5%, respectively until the participants reach volitional exhaustion. The entire exercise testing protocol (metabolic economy plus VO2max) will last 20-25 minutes.

**Dietary food records, exercise tracking, continuous glucose monitoring (CGM), and 24-hour urine collection:** Following laboratory testing, participants will be instructed on completing 3-day food records and exercise tracking, performing the CGM and completing the 24-hour urine collection. Participants will be asked to record all of the food they eat for 3 days, rate feelings of hunger and appetite using standardized appetite rating sheets, and wear a smart watch over this same time period. At baseline only, they will be asked to complete a food-frequency and lifestyle questionnaire specific to vitamin D intake/status simultaneously with the 3-day food records. The smart watch will use an app to measure heart rate and estimate energy expended during structured exercise or physical activity; this will be used to help estimate the participants total energy expenditure. It will be necessary to have the GPS function turned on during the collection of physical activity data but only data related to time, distance or intensity and not GPS coordinates will be downloaded or recorded. CGM will also coincide with the three-day food records using a device called a “Continuous Glucose Monitor” that is typically worn on the back of the upper arm. This requires that a small amount of interstitial fluid (0.5 microliters) be sampled every 15 minutes (96 times per day) throughout the course of the 3-day measurement. In addition, participants will be asked to collect urine for 24 hours during one day of this recall or within the first week of the study. Participants will void and discard the first morning urine sample and then collect all subsequent samples in provided clinical urine jugs for 24 hours, ending with the first sample upon waking the next day. Participants will schedule a time to drop off their urine during one of their resistant training sessions the first week or at a separate time, if it is more convenient. The instructions the participants will receive on using the Smart Watch, using CGM, and collecting the 24-hour urine are uploaded as an Addendum.

